6.6.2 Methods of data selection

Original result (OR) analysis

Original result analysis implies the analysis of data exactly as observed. OR analysis will be performed on endpoints that are either not affected by patients' antidiabetic rescue medication use or if it is not meaningful to apply any imputation rule on them for replacing the missing values.

Observed cases (OC) analysis

For all efficacy endpoints, it is planned to analyse only the available data that were observed while patients were on treatment, i.e., excluding the missing data. In other words, OC analysis will be performed and missing data in this analysis will not be replaced.

For all efficacy endpoints, this OC-technique will set all values measured after antidiabetic rescue medication taken to missing (antidiabetic rescue medication as defined in [section 6.6.1](#)).

Observed cases analysis including data after treatment discontinuation and rescue therapy (OC-AD)

To mimic an intent-to-treat (ITT) analysis, post-treatment as well as post-rescue measurements may also be included. This will be done as a secondary analysis of the primary endpoint with OC as the imputation rule.

Non-completers considered failure (NCF)

For binary endpoints, like a treat to target response of $\text{HbA1c} < 7.0\%$, a conservative method to replace missing values is to consider them as "failures". Missing data due to early discontinuation per the completer definition will be replaced as "failure" (i.e. $\text{HbA1c} \geq 7.0\%$) up to the planned final visit to be reached by all patients. Values obtained after rescue medication was started are also replaced as "failure".

A multiple imputation (MI) approach will also be used as a sensitivity analysis for the primary endpoint. Further details can be found in [Section 7.4.2](#).

6.6.3 Safety and other variables

Missing safety data will not be replaced.

Proprietary confidential information © 2021 Boehringer Ingelheim International GmbH or one or more of its affiliated companies

An analysis of the changes from baseline to the last available value under treatment and the minimum and maximum post baseline will be determined for quantitative safety laboratory variables.

6.6.4 Missing dates and times

Missing or partial date information for AEs will be replaced according to general BI rules described in the BI guidance for handling of missing and incomplete AE dates [\(1\)](#).

If the date of first drug administration is missing but the patient was randomised, the date of the first drug administration will be set to the date of randomisation. If the date of first administration is partially missing with the month and year present, the day will be set to the date of randomisation if randomisation was in the same month. If randomisation was in the month prior to the first drug administration the missing day will be imputed as the first day of the month.

A missing time of first drug administration will be imputed as 12:00 o'clock noon, missing administration times at on-treatment visits will be imputed by 08:00 o'clock in the morning.

As a general rule, a missing drug stop date will be imputed according to the following principles:

- If an End of Treatment (EoT) visit, visit 8, is documented, it should be the date of the EoT visit
- If the date is incomplete with only month and year and the EoT visit is missing, it should be the first day of the following month.
- If the patient is lost to follow-up, it should be the date of the last visit + the longest treatment duration based on drug supply + 1 day.
- If a patient died during the course of the trial and no additional information about drug stop date are available, the date of death will be used as drug stop date assuming that the patient took the medication until the day of death.
- All other cases need to be assessed by the trial team on an individual basis, trying to use the points above as guidance.

For partial start and stop dates for concomitant therapies (CT) and additional antidiabetic drugs, the following derivations will be used to impute 'worst case' values.

- If the day of the end date is missing then the end date is set to last day of the month.
- If the day and month of the end date are missing then end date is set to 31st December of the year
- If the day of the start date is missing the start date is set to first day of the month
- If the day and month of the start date are missing then the start date is set to 1st January of the year.

All other cases need to be assessed by the trial team on an individual basis, using the above points as guidance.

In case of missing visit date for a compliance record, the following hierarchy will be used to select a date to impute the missing visit date:

- The visit date registered in the IRT system
- The date of the vital sign measurement for the same visit

Proprietary confidential information © 2021 Boehringer Ingelheim International GmbH or one or more of its affiliated companies

- The date of the safety laboratory sampling for the same visit

All other cases need to be assessed by the trial team on an individual basis, using the above points as guidance.

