#### Hyperglycemia

If the following FPG criteria in [Table 4.2.1: 1](#) are met and confirmed, investigators may increase the insulin dose for the treatment of hyperglycemia according to their discretion and the change should be documented in the eCRF [[R08-2669](#)].

The first choice of rescue therapy should be the adjustment of insulin therapy. Its dosage will be left to the discretion of the investigator. However the insulin regimen and daily number of injections should remain unchanged. In very rare cases, adjustment of background therapy or addition of another oral anti-diabetic medication except SGLT-2 inhibitors would be appropriate. Such cases should be discussed with the Manager (CTM) or the Clinical Trial Leader (CTL).

Table 4.2.1: 1 FPG criteria for hyperglycemia

Week	Visit	FPG level
Week 1- 4	up to Visit 4 (included)	>270 mg/dl (>15.0 mmol/l) after overnight fast
Week 4-12	up to Visit 6 (included)	>240 mg/dl (>13.3 mmol/l) after overnight fast
Week 12-24	after Visit 6 until Visit 8	>200 mg/dl (>11.1 mmol/l) after overnight fast

To confirm the above results, there should be a minimum of two measurements, at least one of which performed after an overnight fast at the investigational site, and on a different day to the initial measurement.

A FPG, HbA1c sample should be taken before initiation of rescue therapy and sent to central lab for analysis. The HbA1c sample is not required if a sample has been taken and sent to the central lab for analysis within the last 4 weeks.

If, in the Investigator's clinical opinion, no further effect from the rescue medication is anticipated, and the patient's hyperglycemia cannot be controlled, the patient should be discontinued from the treatment as specified in [section 3.3.4](#).

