**Visits 4-8/EOT**

Visits should be performed as mentioned in the Flow Chart and the respective protocol sections.

- Collection of urine and blood for laboratory testing must be performed prior to

Proprietary confidential information © 2021 Boehringer Ingelheim International GmbH or one or more of its affiliated companies

administration of study medication according to the Flow Chart

- All the patients including the treatment discontinued should perform the MTT and follow the process described in [Section 5.1](#)
- Blood pressure should always be measured before taking any blood sample, details see Appendix 10.1
- Collect returned medication prior to dispensing new medication
- Collect the HBGM test log
- New medication kit must be dispensed according to the Flow Chart, and IRT must be contacted at those visits to obtain medication kit numbers to be dispensed
- Patients should be reminded about the importance to follow the agreed diet and exercise plan.
- Instruct patient NOT to take study medication as well as background medications on the morning of trial visits as described in section 4.1.4
- Instruct patients to perform 8-point glucose profile within one week prior to visits as indicated in the Flow Chart
- Visit 8/EOT is the last visit of the treatment period. Study medication will not be dispensed at Visit 8/EOT

If a patient prematurely discontinues from the 24-week treatment period, the patient must return to the trial site for EOT (within 7 days of stopping study treatment) including MTT. The reason for premature trial drug discontinuation must be documented in the eCRF. In addition patients will be encouraged to attend all subsequent planned onsite visits despite not being under treatment anymore and perform all study procedures. If the EOT visit occurs within the time window of a planned visit, the EOT visit will replace the planned visit.

The need for coming to future visits in case of premature discontinuation of trial medication will be explained to patients prior to their participation in the trial.

The investigator may initiate any additional antidiabetic therapy for the patient, based on his or her discretion, no sooner than one day after discontinuing study medication or after Visit 8. Patients who prematurely discontinue the study should be registered as discontinued, and patients who complete the full 24-week double-blind treatment period should be registered as completed in the IRT.

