### **6.2.3 Follow-up period and trial completion**

For all patients completing the study according to protocol or prematurely discontinued without persisting AE at Visit 8, a follow-up contact (Visit 9) with the patient (preferably by phone) should be done by the investigator at the end of the followup period of 7 days. The following should be confirmed and recorded at Visit 9:

- Concomitant therapies
- Any AEs
- HBGM result

For patients completing the study according to the protocol or prematurely discontinued from the 24 week treatment period however, agree to return, with persisting AE at Visit 8, the following examinations should be performed at Visit 9 additionally:

- Vital signs
- Collection of blood and urine samples for safety laboratory evaluation
- FPG

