6.6.1 Definition of rescue therapy for censoring

For some of the imputation methods defined below, values after first rescue medication will be set to missing. In this context, the following three situations are defined as use of rescue medication:

- Additional antidiabetic medication used for ≥ 7 consecutive days
- For insulin, a change of $>10\%$ (increase/decrease) from the last dose recorded prior to the baseline visit (Visit 3) taken for ≥ 7 days
- For OADs, a change in dose (increase/decrease) compared with the baseline dose for ≥ 7 consecutive days

This approach will be used when considering which data to exclude from the OC analyses.

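### SAP 6.6.4 back-dates a partly recorded start of an antidiabetic drug with no lower bound, so a drug begun after Visit 8 can delete a valid Week 24 HbA1c

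*SAP*

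**What the plan says.** **The date rule.** SAP 6.6.4 has a worst-case rule: "For partial start and stop dates for concomitant therapies (CT) and additional antidiabetic drugs, the following derivations will be used to impute" such values. For start dates, "If the day of the start date is missing the start date is set to first day of the month", and "If the day and month of the start date are missing then the start date is set to 1st January of the year". No lower bound is given. Individual assessment by the trial team is reserved for cases the listed rules do not cover, and month-only and year-only dates are the listed cases. The same section does bound a partial date of first study-drug intake: it uses the randomisation date when the months agree.

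**The censoring rule.** SAP 6.6.1 says "values after first rescue medication will be set to missing" for some methods. It counts as rescue any additional antidiabetic drug used for at least 7 consecutive days, and does not limit this to starts before Visit 8. Under SAP 6.6.2 the observed-cases (OC) method drops every efficacy value after rescue, and the non-completers-considered-failure (NCF) method turns such values into failures. OC is the primary analysis (SAP Table 6.3:1 and 7.4.1).

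**Therapy after the last treatment visit.** Protocol 6.2.2 lets the investigator add antidiabetic therapy "no sooner than one day after discontinuing study medication or after Visit 8". Protocol 6.2.3 then requires that "a follow-up contact (Visit 9) with the patient (preferably by phone) should be done by the investigator" at the end of the 7-day follow-up, with concomitant therapies recorded.

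**The concern.** A drug started after Visit 8 cannot have influenced the Week 24 HbA1c. With a full date it censors nothing. The same drug recorded by month only can be moved to before Visit 8, and the Week 24 value is then removed as post-rescue. The imputation rule alone makes the difference.

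The rule also lengthens the apparent duration of use, so it can create the rescue episode as well as misplace it.

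At stake are observed on-treatment values of the primary endpoint at the visit on which the confirmatory contrasts are made. The other continuous efficacy endpoints analysed by OC, and the responder endpoint, are exposed in the same way. For a patient who stops early, a drug started after the EOT visit can likewise remove the on-treatment value taken at that visit.

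**Working it through.** **1. Worked example.** Visit 8 is on 12 June, the drug starts on 15 June, and the record says June.
- Imputed start: 1 June, which is 11 days before Visit 8.
- Visit 9 is 7 days after Visit 8, on 19 June. True use to Visit 9 is 15 to 19 June, or 5 days, below the 7-day threshold. Imputed use is 1 to 19 June, or 19 days, above it.
- Result: the 12 June HbA1c is missing in OC and a failure in NCF.

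**2. Month-only dates: how often the imputed start precedes Visit 8.** Take each day of a 365-day year as a possible Visit 8 date, with the true start k days later. The imputed start is strictly before Visit 8 unless Visit 8 falls in the last k days of a month (12k dates; the imputed start is then later) or on the first of a month (12 dates; the two coincide). The count is 365 − 12k − 12.
- k = 1: 365 − 12 − 12 = 341 (93%)
- k = 3: 365 − 36 − 12 = 317 (87%)
- k = 7: 365 − 84 − 12 = 269 (74%)

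These shares are conditional on a new drug being started in that week and on its day being unknown. They are not rates of harm.

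**3. How much is lost.** The largest back-shift before Visit 8 is 29 days. In the Flow Chart, Visit 7 can fall as late as day 127 + 7 = 134 and Visit 8 no earlier than day 169, a gap of 35 days. A month-only date therefore normally costs the Week 24 value only.

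**4. Year-only dates** (true start 1 day after Visit 8, Visit 3 set 168 days before Visit 8). 1 January precedes Visit 8 for 363 of 365 dates. For 167 it falls within the treatment period and can remove earlier visits too. For 196 it falls on or before Visit 3, and the SAP does not say how such a drug is classified.

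**5. The plan's sample size.** Inputs from Protocol 7.5: difference 0.62%, SD 1.1%, two-sided alpha 0.05, censoring rate 0.08, information content 0.4. A two-sample t-test with 68 per arm has power 90.4% (stated: 90.3%). Then 68/(1 − 0.08 × 0.6) = 68/0.952 = 71.4, rounded up to 72. The plan's figures reproduce.

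**6. Power if x completers per arm are wrongly censored.** Effective n = 72 × [1 − 0.6 × (0.08 + x/72)] = 68.5 − 0.6x. The values of x are assumptions, applied equally to all arms.

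| x per arm | Effective n | Power |
|---|---|---|
| 0 | 68.5 | 90.6% |
| 1 | 67.9 | 90.3% |
| 3 | 66.7 | 89.8% |
| 5 | 65.5 | 89.3% |
| 10 | 62.5 | 87.8% |

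One completer is 1/72 = 1.4% of an arm.

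**The case against.** **The event should be rare.** The investigator starts the post-Visit 8 drug, follow-up lasts only 7 days, and Protocol 8.3.1 lists start dates of concomitant therapy among the source data. A site would have to lose, within days, the date of a drug it had just started. Nor does the existence of a rule imply that such dates are expected: the rule covers all concomitant therapies, including drugs begun before the trial, where partial dates are ordinary. This stands, and it is why the size is put as small.

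**Earliest-date imputation is deliberately cautious.** It avoids keeping values that were truly post-rescue, and for a drug started during treatment it is defensible. Only the missing floor is at fault.

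**There is a check.** The OC-AD analysis keeps post-rescue values and is immune, and the MMRM still uses the patient's earlier visits. Both are true, but the confirmatory test rests on OC.

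Three stronger readings are tempting, and the documents do not support them.

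- *That the loss falls mainly on placebo and biases the comparison.* Nothing says placebo patients receive more new therapy after Visit 8. Study drug stops for everyone then, and investigators remain blinded. Completers with HbA1c of 7.0% or more are non-responders already, so NCF changes nothing for them.
- *That pre-rescue HbA1c samples are routinely deleted.* Protocol 4.2.1 says a "sample should be taken before initiation of rescue therapy and sent to central lab for analysis", but waives the HbA1c if one was sent within the last 4 weeks. SAP 6.7 analyses one value per window, which may be another sample. The preferred rescue is insulin adjustment, and an added oral drug is described as very rare.
- *That early rescue is often dated before the first dose.* A rescue in the month of randomisation could be, but up to Visit 4 it needs confirmed FPG above 15.0 mmol/L in patients who were excluded above 13.9 mmol/L during run-in. The case is remote.

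**Conclusion.** The point holds as a low-frequency correction. As written, SAP 6.6.4 with 6.6.1 and 6.6.2 gives a wrong result in a foreseeable case: a drug started after Visit 8 or the EOT visit with its day unknown is usually dated before that visit, and a valid on-treatment HbA1c is dropped from the primary analysis and counted as a failure in NCF.

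The number of patients cannot be derived, because the documents give no rate of partial dates. On an assumed 1 to 5 completers per arm, power is about 90.3% to 89.3%, against 90.6% with none. That calculation gives each wrongly censored completer the plan's information content of 0.4. No direction of bias is shown: removing an observed value from a missing-at-random model has no fixed sign, and no arm imbalance is documented. The reason to act is that the rule decides which primary-endpoint values exist and is easily corrected before unblinding.

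**What to change.** In SAP 6.6.4, for additional antidiabetic drugs, impute the earliest start consistent with the record, namely the later of:

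- (a) the first of the month, or 1 January if the month is also missing; and
- (b) the day after the last visit whose concomitant-therapy check did not record the drug.

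A drug first recorded at Visit 9 then cannot start before the day after Visit 8, and a drug not recorded at Visit 3 cannot start before the first randomised dose. If floor (b) falls after the recorded month or year, send the case to blinded team review. Before unblinding, list every patient censored on an imputed date.

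The cost is two sentences in the SAP and a small programming change. No new data are needed: the Flow Chart has concomitant therapy checked at every visit, and Protocol 10.2 keeps that check for remote visits. One limitation is that a drug overlooked at a visit would be dated too late. The pre-unblinding listing shows which patients were censored on imputed dates, so those cases can be reviewed.

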6.6.5 Values below/above limits of quantification

For biomarkers (C-peptide, insulin) reported values below the limit of quantification (BLQ) will be replaced with 2/3 times lower LQ. This is approximately the median of the expected ‘true’ value if the biomarker follows a normal distribution. The inverse of the factor 2/3 will be used to replace values above the upper LQ, resulting in 1.5 times upper LQ. The analysis dataset will contain flags to indicate that the value was BLQ and a variable for the value of the LQ. With this approach, even a change of the method with different LQs can be handled within a trial. The number of samples above and below the limit of quantification will be included in the biomarker tables.

6.6.6 HOMA- β

Please refer to CTP Section 5.4.1 for the definition of HOMA- β . For FPG values <3.5 mmol/L, HOMA- β assumes extreme negative values for FPG values only slightly smaller than 3.5. For FPG=3.5 mmol/L, the ratio is not defined. Therefore, HOMA- β will only be calculated for FPG >3.5 mmol/L and set to missing for lower values.

6.7 BASELINE, TIME WINDOWS, AND CALCULATED VISITS

With regard to efficacy and safety endpoints, the term “baseline” refers to the last observed measurement prior to administration of any randomised study medication.

Measurements taken prior to the first intake of randomised study medication will be considered pre-treatment values. Pre-treatment values will be assigned to a visit according to the nominal visit number as recorded on the eCRF or as provided by the laboratory.

In general, the date and clock time of the first drug administration will be used to separate pre-treatment from on-treatment values; Measurements taken after the first intake of randomised study medication will be considered on-treatment values if they have been obtained up to end of the parameter specific follow-up period as defined in [Table 6.7:1](#) below and will be assigned to the randomised study medication for efficacy analyses and to the first study medication taken for safety analyses.

Proprietary confidential information © 2021 Boehringer Ingelheim International GmbH or one or more of its affiliated companies

Table 6.7:1 Endpoint specific follow-up period for the assignment to treatment phase

Endpoint	Last day of assignment to treatment phase (days after study medication stop date)
Efficacy	
HbA _{1c}	7
FPG	1
Body weight	1
Blood pressure (systolic, diastolic)	1
PPG	1
MDG	1
C-peptide	1
Biomarkers of insulin resistance and secretion	1
Waist circumference	7
Safety	
Adverse events	7
Safety laboratory measurements	3
Pulse rate	1

Measurements taken after the end of the endpoint specific follow-up period and after the last intake of study medication will be considered post-treatment values.

On-treatment efficacy and safety measurements will be assigned to visits based on time windows around the planned visit dates. These time windows are defined based on the planned number of days after the date of first administration of study medication (see [Table 6.7:2](#)).

Proprietary confidential information © 2021 Boehringer Ingelheim International GmbH or one or more of its affiliated companies

Table 6.7:2 Time windows for on-treatment efficacy measurement scheduled for each on treatment visit

Visit number	Visit label	Planned days	Time window (actual days on treatment)	
			Start	End ^A
3	Baseline	0	NA	1 ^B
4	Week 4	28	2	42
5	Week 8	56	43	70
6	Week 12	84	71	105
7	Week 18	126	106	147
8	Week 24/EOT	168	148	Study medication stop date + X days

^A In case of premature discontinuation of the study medication an early EoT visit has to be performed. If such an EoT Visit falls into the time window of a previous visit, measurements will be assigned to this previous visit and the visit value will be determined as described below. In this case the time window for the visit that includes the early EoT visit will end X days after the study medication stop date, including Day X. The definition of X is endpoint specific, cf. [Table 6.7:1](#). Patients will then be asked to continue in the study according to the visit schedule. Off-treatment measurements will be assigned to visits in the same manner. No time window for optional visit is planned.

^B Only values taken prior to the start of treatment with randomised study medication can be considered baseline values. Time windows will be used for assignment of measurements to scheduled visits.

Reasons to base the time windows on the actual treatment start date rather than the randomisation date are:

- If first intake of study medication shows a large delay by e.g. more than one week after the date of randomisation, a measurement taken four weeks after randomisation rather reflects the drug effect after three weeks than after four weeks and thus may underestimate the treatment effect at this visit.
- With large delays of the introduction of study medication after the randomisation, the time window for the first on-treatment visit could include times the patient was not yet on study medication.

The time window for the first visit after randomisation starts on the day after the first intake of study medication. This maximises the number of measurements used in by visit analyses may lead to an underestimation of the treatment effect at the first visit for parameters that react slowly on treatment.

The midpoint between two on-treatment visits defines the end of a time window, with the midpoint being included in the time window of the preceding visit. The end of the time window of the last on-treatment visit (end of treatment (EoT)) is endpoint dependent ([Table 6.7:1](#)).

Repeated and unscheduled efficacy and safety measurements will be assigned to the nominal visits and listed in the SDL according to the time windows described above. Only one observation per time window will be selected for analysis at an on-treatment visit - the value

Proprietary confidential information © 2021 Boehringer Ingelheim International GmbH or one or more of its affiliated companies

will be selected which is closest to the protocol planned visit day. If there are two observations which have the same difference in days to the planned day or if there are two observations on the same day, the first value will be used. If an observation is available on the last day of treatment, this observation will be preferably selected over any later observation that is still within the time window (not applicable for standard laboratory summaries). If there are multiple values within the time window of the last visit, including a value on the last day of drug intake, the value on the last day of drug intake is used as the value of the last visit.

Data prior to randomisation will be based on nominal visits and time windowing will not be applied. For these time points, data from the scheduled visit will always be selected if they are collected correctly. Unscheduled visits will only be considered if no correct data from the scheduled visit is available. If no correct data from a scheduled visit is available and multiple unscheduled correct values are available for a visit, the first correct value will be selected.

